3.3 Secondary Objectives

Secondary objectives of the feasibility trial are to estimate the:

- **3.3.1** acceptability of randomisation and the StopApp intervention for participants
- **3.3.2** acceptability of primary and secondary outcome measures and measures required for cost-effectiveness and cost utility analyses in a future trial
- **3.3.3** key costs which would be incurred in delivering the intervention and usual care, including a comparison of non-attendance at SSS (Did-not-attend or DNA rates) between each arm of the trial.
- **3.3.4** feasibility of accessing SSS and GP data (if recruited via GP) on attendance, quit dates set and four-week quits for trial participants
- **3.3.5** any differential recruitment and attrition rates across socio-economic groups and age and gender
- **3.3.6** rate of SSS attendance in the treatment and control groups to estimate the event rate of the primary outcome measure for a future trial and support future trial sample size calculations

4. Methodology

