PharmOutcomes/Outcomes4Health – this application is not owned by CU, not hosted on the CU server and not integrated with any of the above applications. It is owned by Pinnacle Health and commonly used for recording data by public health and primary care service providers. CU have carried out due diligence checks and confirmed that its processes are GDPR compliant. PharmOutcomes/Outcomes for Health is used by Stop Smoking Services in Warwickshire to record data on patient attendance at stop smoking appointments, guit dates and 4-week guit rates (stop smoking data). When an intervention participant using the stopapp decides that they would like to book a stop smoking service appointment and clicks on 'book now' they reach a map/service search page that asks for a postcode or town name, after the stopapp user enters the information and clicks search, the API that connects stopapp to PharmOutcomes/Outcomes4Health draws live information about which services are currently offering appointments near that location and presents the sites for the user to select from. When a site is selected, the API connecting stopapp and PharmOutcomes/Outcomes4Health pushes information from the calendar function in PharmOutcomes/Outcomes4Health about which appointments are available. The stopapp user can select a preferred time and date and an alert is sent to the relevant service provider within PharmOutcomes/Outcomes4Health about the appointment request for them to respond to. Service providers then use the PharmOutcomes or Outcomes4Health system to record all further information about the users' engagement with the service as they would for any other service client.

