We will receive data for each of our participants who consented from PharmOutcomes and Outcomes4Health on whether or not they booked an appointment, whether or not they attended an appointment, whether or not they set a quit date and whether or not they achieved a 4 week quit including whether or not this was CO verified. The stop smoking service data will be sent to a secure NHS.net email address held by one member of the research team, in report format, and will include only trial participants who consented to the research team being sent information about their SSS use. This data will be recorded by hand by a researcher directly into a spreadsheet alongside each participant's unique ID generated by eNgage. Each participant's name will be used to link the data (unique ID and stop smoking data) but will not be recorded within the database. Coventry University is currently developing a data sharing agreement with Warwickshire Public Health and Pinnacle Health for this purpose. Recruitment will not begin until this (as well as all other ethics and governance approvals) is in place.

A drop-down box within the Pharmoutcomes/Outcomes4Health appointment data input form used by SSS staff, will include a compulsory prompt to staff to ask whether their client is taking part in the MyWay research project/study (with details of the trial to help recall). If the client answers yes, they will be asked if they agree (consent) to the researcher's contacting the service to collect information about their use of the service, with a 'YES/NO' drop-down box. This acts as a proof of participant consent for Pinnacle health, in order to generate a report of trial participants who provide consent only.

Downloaded data - on completion of data collection, the following will occur:

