4.10.2 Two month follow-up

Follow up emails will be sent approximately two months after completion of the baseline questionnaire, to invite participation in the follow-up questionnaire. Emails containing a link to the follow-up measures will be sent to all participants to assess feasibility and acceptability of these, and likely attrition rates in a future trial. The questionnaire will also ask them to confirm whether they booked an appointment and attended a SSS, set a quit date and reached a 4-week abstinence, and explain what prompted them to book an appointment. Pinnacle Health Ltd will run a search of the PharmOutcomes and Outcomes4Health systems for our participants (where they consented to this) and provide us with their service use data to test feasibility of sourcing objective evidence of booking, attendance (and did not attends; DNAs), guit dates set, and CO tested 4 week guits. We will also assess feasibility and acceptability of follow-up measures of; motivation using the MTSS and a single item Likert scale (Hummel et al., 2017); the EQ5D-5L instrument; the ICECAP-A instrument and a resource use questionnaire to capture participant use of NHS and other resources for both intervention and control arms. Non-responders to the email will be contacted two weeks later with a reminder to respond. We will send an email with a link to the information leaflet provided to the control group, to anyone who contacts us after the end of the period of recruitment to the study until the end of December 2019.

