5.1 Risks and benefits

Risks - Participating in the proposed research has limited risk associated with it for participants. Consenting to participate will require participants to complete questionnaire measures and to access either an online information leaflet or the StopApp intervention. They will be required to make a decision about whether or not to book and then attend a SSS appointment and may then choose to go to that appointment, set a quit date and attempt to stop smoking. Risks associated with these actions are in line with normal every day risk and we will provide all study participants with information about how to access support for anything related to their participation in the study. Some smokers may attempt to quit and fail and this may have some negative psychological impacts in the short-term. Participants will also need to provide consent for data held about them and their smoking status by their GP and SSS to be accessed during the study. All such data will be handled in accordance with the latest data protection legislation and anonymised for the purposes of data analysis and reporting.

Potential benefits - There is the potential that some smokers who participate may actually quit smoking which has benefits to them and society. In addition, each quit attempt a smoker makes means they are a step closer to quitting for good (West, 2013) and so there is an overall long-term net benefit to this outcome should it occur.

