5.2 Ethical arrangements

Ethical approval will be obtained via the Health Research Authority (HRA), Warwickshire County Council (who commission the SSS) and Coventry University. No potential participants will be contacted until all ethical and R&D approvals are in place.

As outlined above, there are no major risks associated with participating in the research. Participating GP surgeries will receive funding via the CRN to send out recruitment communications to smokers on their patient lists. Participant Information

details and clear consent statements will be available on the eNgage study websites (for feasibility study and qualitative process evaluation) providing a full explanation of the research and what participation involves. Only those who actively opt in to the study and provide full informed consent to participate will able to participate. Participants in the feasibility RCT will be asked explicitly to consent to access to information about their smoking status and records via their GP and/or SSS (this is not mandatory for participation). Only where they have explicitly provided written consent for this will the research team gain access to this information. Participants will be made fully aware of their right to withdraw from the research up to the point of data analysis without needing to give a reason. They will be made aware of exactly how to go about this and all data provided by them will be withdrawn from the dataset and destroyed. Information about the confidentiality and anonymity of their data will be made absolutely clear to participants and we will tell people how their information will be treated and stored and what we will be doing with this. We will ensure that all use of data complies with the most recent data protection requirements and that information governance protocols are strictly adhered to. Participants will be given sources of information, advice and support in relation to issues that being involved may raise for them.

6. Stop/go criteria

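### The protocol gives two unreconciled rules for releasing stop smoking service records; if the staff prompt governs, people who book and do not attend may go unrecorded, possibly unequally by arm

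*Protocol*

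**What the plan says.** The protocol describes release of service records in two ways.

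- **Staff prompt (4.9.2).** The appointment form in PharmOutcomes/Outcomes4Health "will include a compulsory prompt to staff to ask whether their client is taking part in the MyWay research project/study". A client who says yes is then asked to agree to release, and staff record YES or NO. The protocol adds: "This acts as a proof of participant consent for Pinnacle health, in order to generate a report of trial participants who provide consent only".
- **Search on trial consent (4.10.2 and 5.2).** At follow-up, "Pinnacle Health Ltd will run a search of the PharmOutcomes and Outcomes4Health systems for our participants (where they consented to this"), and bookings, attendances, DNAs, quit dates and four-week quits are expected back. Section 5.2 says RCT participants are asked explicitly for access to GP and service records, and that "this is not mandatory for participation". Section 5.1 reads differently: "Participants will also need to provide consent for data held about them and their smoking status by their GP and SSS to be accessed".

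Section 4.9.2 also expects booked-or-not and attended-or-not for every consenting participant.

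Booking routes differ by arm. A StopApp user picks a slot online, after which "an alert is sent to the relevant service provider within PharmOutcomes/Outcomes4Health about the appointment request for them to respond to" (4.9.2). The control leaflet has no online booking link (4.7), and 4.10.3 gives telephone calls as an example of how usual-care bookings are made.

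Three uses depend on these records. Objective 3.3.3 covers costs, "including a comparison of non-attendance at SSS (Did-not-attend or DNA rates) between each arm of the trial", and 4.10.3 names the service systems as the source of DNA data. Section 4.12 uses the booking and attendance differences to support the sample size of the definitive trial. Objective 3.3.6 is the attendance event rate.

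**The concern.** The staff prompt works only if staff speak to the client. Someone who books online and does not attend may never have that conversation, and the protocol describes no other way for that person to enter a report built on the prompt. A DNA is by definition a client who did not come, so it is the outcome most exposed to this rule.

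The chance of being asked may also depend on the booking route, which the intervention changes. A control client who telephones could be asked during the call, while a StopApp user who books on screen might not be. A difference in recorded DNA or booking rates could then partly reflect who was asked.

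At stake are the between-arm DNA comparison, the record-based booking difference carried into the next trial's sample size, and possibly the attendance event rate. The answer to 3.3.4, on feasibility of access to service data, would also describe how the prompt performed and not what enrolment consent could deliver.

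**Working it through.** The protocol states no figure on this point, so there is nothing to reproduce. The check has two parts.

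**1. The text side by side**

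| Question | Staff prompt (4.9.2) | Search (4.10.2, 5.2) |
|---|---|---|
| Who gives consent, and to whom | Service client, to service staff | RCT participant, to the trial |
| Needs contact with service staff | Yes | No |
| Route for an online booker who never attends | None described | Yes, if a record exists and matches |
| Role of the other consent | Not stated | Not stated |

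The protocol does not say whether the two consents are alternatives or both required, or whether the appointment form is completed at booking or at the visit.

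**2. Size if the staff prompt governs**

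Let b be the true booking rate, d the true DNA share among bookers, a the share of attenders flagged YES and f the share of non-attenders flagged YES.

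- Recorded booking rate = b × [(1 − d) × a + d × f]
- Recorded DNA rate = d × f / [(1 − d) × a + d × f]

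The recorded DNA rate is below d whenever f is less than a. A false between-arm DNA difference needs flagging that differs by arm.

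The protocol gives no value for b, d, a or f, so all are assumptions. Every attender is taken as flagged (a = 1).

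*True DNA 40% in both arms, true bookings 25% against 15% (difference 10 points):*

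| Non-attenders flagged, StopApp / control | Recorded bookings | Difference | Recorded DNA |
|---|---|---|---|
| 100% / 100% | 25.0% / 15.0% | 10.0 | 40% / 40% |
| 50% / 50% | 20.0% / 12.0% | 8.0 | 25% / 25% |
| 0% / 0% | 15.0% / 9.0% | 6.0 | 0% / 0% |
| 0% / 50% | 15.0% / 12.0% | 3.0 | 0% / 25% |
| 0% / 80% | 15.0% / 13.8% | 1.2 | 0% / 34.8% |

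For example, control at 50% flagged: 15 × (0.6 + 0.4 × 0.5) = 12.0%, and DNA = 0.2/0.8 = 25%.

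*Equal true bookings of 20%, true DNA 40%:* the recorded difference is 0 with equal flagging, 12.0 − 16.0 = −4.0 points with 0% / 50% flagged, and 12.0 − 18.4 = −6.4 points with 0% / 80%.

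*True DNA 30%, bookings 25% against 15%:* with no non-attender flagged, 17.5 − 10.5 = 7.0 points. With 0% / 50% flagged, 17.5 − 12.75 = 4.75 points, and DNA reads 0% against 0.15/0.85 = 17.6%.

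*Attendance* is affected only if some attenders are not flagged. Section 4.11 uses a 7-point difference; take 17% against 10% as an assumption. With 80% flagged in both arms, 13.6 − 8.0 = 5.6 points. With 90% StopApp and 60% control, 15.3 − 6.0 = 9.3; reversed, 10.2 − 9.0 = 1.2.

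*Counts.* With 162 randomised 1:1, about 81 per arm, the first set of assumptions gives 81 × 0.25 × 0.4 = 8.1 and 81 × 0.15 × 0.4 = 4.9 true DNAs. Losing a few of them changes the result.

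**The case against.** A reader might infer that records come only through the staff prompt, that online non-attenders can never appear, and that the comparisons are therefore biased by design in a known direction. The documents do not support that.

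- Section 4.10.2 describes a search and expects DNAs from it, and 5.2 describes consent given as a trial participant. The fault is two accounts that need reconciling, not one settled rule. The consent condition in 4.10.2 does not say which consent it means, so the two might even be cumulative.
- The timing of the form is unstated. Providers must respond to each online request, and section 7 says StopApp passes on name and mobile number, so staff could contact the client first.
- That control clients are asked during a booking call is an inference from a costing example. If the form is completed at the visit, DNAs are lost in both arms: the rate is understated, but no false DNA contrast arises.
- The prompt is compulsory and carries trial details to aid recall. Unequal recall between arms is conjecture.
- Not everything comes from this report. The two-month questionnaire asks about booking and attendance, and 4.12 reports self-reported results by arm. A DNA could be inferred among responders.
- The primary objective is recruitment and attrition, the stop/go criterion is 1.8 participants per day, and testing access to service data is itself an objective.

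All of this stands and limits the claim. It does not settle which rule applies, and self-report does not cover non-responders.

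**Conclusion.** The concern holds in limited form. The two descriptions of record release conflict or are at least unreconciled. If the staff prompt is required, people who book and do not attend without speaking to staff have no described route into the report, so record-based DNA rates and bookings are understated. The loss may differ by arm because booking routes differ, but its direction and size rest on flagging rates the protocol does not give.

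Under the assumptions shown, a true 10-point booking difference is recorded as anything from 8.0 down to 1.2 points, and an equal 40% DNA rate as anything from 25% in both arms to 0% against 34.8%. These are illustrations, not estimates.

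The secondary DNA comparison (3.3.3), the record-based booking difference (4.12) and possibly the attendance event rate (3.3.6) are affected. The primary objective and stop/go rule are not. This should be fixed; it does not threaten the study's main purpose.

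**What to change.** 1. State in 4.9.2, in 4.10.2 and in the data-sharing agreement that the explicit, optional consent to service-record access given at enrolment triggers the search. It should cover all consenting participants in both arms and return bookings, attendances and DNAs, with consenters as the denominator.
2. Match on name plus a second identifier already held for everyone, such as baseline postcode or registration email, and have the consent statement cover that use. Check that the provider holds the same item: section 7 says StopApp passes on only name and mobile number, and the trial asks for a telephone number only from people interested in interview.
3. Report unmatched participants and run a sensitivity analysis. Do not treat a missing record as no event, because failed matches would then count as non-attendance.
4. Keep the staff prompt as a secondary check. If the system owner still requires it, say that record-based DNA and booking contrasts will not be interpreted between arms.
5. Reconcile 5.1 with 5.2 on whether consent to record access is required or optional.

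The cost is revised consent and agreement wording, and disclosure of one identifier to the provider. No extra participants or visits are needed. The agreement is still being developed and recruitment waits on it (4.9.2), so the change is cheap now; unflagged non-attenders may not be recoverable later.

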4.9.3 Withdrawal of data

All participants will be informed that they have the right to withdraw their data from the study up to the point at which it is downloaded for analysis and used to create the study linked database (30th June 2019; step 5 above). Participants will be informed that should they wish to withdraw from the study they should contact the research team using the project email address (details provided on eNgage and within email communication to participants). If such a request occurs, the research team will clarify the name and email of the participant, identify their unique participant ID and

then delete all of their data (1-5 as applicable above). The research team will then inform the participant by email that this action has been performed (giving the date/time). The name/email addresses of participants who have withdrawn will be removed from Qualtrics to prevent further auto-generated emails being sent. A datafile logging the date/time of participant withdrawals will held by the lead researcher.

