3.2 Primary Objective

To conduct a feasibility trial of StopApp to estimate recruitment and attrition rates of participants across three settings: GP surgeries, community settings and on-line; at baseline, intervention access, and two-month follow-up.

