On 'joining' a project, eNgage directs participants to Qualtrics to complete baseline measures. The participant's email address is transmitted by eNgage to Qualtrics to enable auto-scheduled email invitations and reminders to be sent throughout the project at relevant time points (i.e. completion of questionnaire and access to intervention). Each participant's unique ID is also transmitted to enable all data collected within eNgage and Qualtrics to be linked (e.g. provision of consent and questionnaire responses).

The randomisation of participants to experimental conditions occurs within eNgage. After each participant has completed their baseline questionnaire within Qualtrics, eNgage will assign condition. Whilst assignment is random, the algorithm applied uses minimisation to ensure balance by factors that are likely to affect SSS access (gender, self-report socio-economic status). Data with respect to these factors is collected for each participant within the baseline questionnaire. On study set-up within eNgage, the research team specify what these factors are and their location within the baseline questionnaire (e.g. Qs1-4). eNgage retrieves this data from Qualtrics and uses it to nominate assignment. eNgage uses the participant's unique ID (sent to Qualtrics previously) to identify the individual. Each participant's response to these questions and condition assignment is additionally stored within eNgage to enable auditing of this process.

Following assignment, participants are directed to the respective intervention or control materials (both stored on the CU server). Analytics data on their use of these materials is collected by Matomo (see below). Following this, participants are directed to complete the follow-up questionnaire within Qualtrics, at 2-months after baseline.

NB. for the My Way study, there will be a number of identical eNgage project pages, one for each of the different recruitment settings. The purpose of this is to enable the unique ID created for each participant to be associated with the type of setting they were recruited from. This is necessary to assess the success of our recruitment strategy across the different settings. The URL for each page will be the only thing that is different for each project page and this will be provided accordingly for those recruited within each of the settings.

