- 1) The eNgage data (to include for each participant: full name, email address, unique participant ID, the date and time consent given, the version of the participant information details they consented to, responses to optional consent questions, responses to randomisation questions and experimental condition assignment) will be retained within eNgage for six years after the end of the study to act as a record of participant consent. This data will be retained in this full form for six years after the end of the study (in case a participant wishes to make a claim against the university in which case both proof of consent plus associated data can be provided). The name and email addresses of those who provided consent (optional) to be contacted about future eNgage studies will be copied into a new datafile (marketing opt-in datafile). This data will be shared with the eNgage lead administrator who will store this on their private password protected OneDrive folder (located on CU server).
- The survey data (baseline and follow-up questionnaire responses collected in Qualtrics) will be downloaded, postcode data removed (to anonymise), and then stored on the team's shared password protected project folder (SharePoint – access rights outlined below; located on CU server)
- 3) Postcode data (taken from baseline survey) and associated unique ID to be downloaded and stored on the research lead's private password protected OneDrive folder (located on CU server). Postcode data to be converted to IMD score. IMD score to be added to downloaded baseline survey data (linked to participant ID). Postcode data will be retained until the end of data processing (data analysed and findings reported) and then deleted.
- 4) The analytics data (from Matomo) will be downloaded and stored on the team's shared password protected project folder (SharePoint – access rights outlined below; located on CU server); NB this data is anonymised IP address masked by default.
- The project stop smoking data will be stored on the team's shared password protected project folder (SharePoint – access rights outlined below; located on CU server)
- 6) In preparation for analysis, data from 2, 3, 4 and 5 will be linked using each participant's unique ID to create the complete datafile in preparation for analysis; initially this will be within Excel format but will likely also be exported

to SPSS (all data will however remain within the shared password protected project folder)

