4.12 Statistical analysis plan

Feasibility and acceptability of all measures will be assessed by level of completeness and by follow-up qualitative interviews with a sub-sample of participants (see detail above on nested qualitative study). We will calculate recruitment rate via GP surgeries as a percentage of those recruited from those smokers identified on participating GPs lists. We will calculate recruitment via community and online settings as the time taken and spend required to recruit 54 participants and/or the number recruited and spend over three months. We will

calculate the average recruitment rate per day across the three settings. We will provide percentage rates for attrition across each recruitment setting at each of baseline, intervention/control access, and two-month follow-up.

We will look at the observed difference between intervention and control groups for bookings and attendance at SSS and use this data to support estimates for the required sample size for a definitive trial. Clinical significance will also be used in these estimates and a comparison of the two will help to determine future trial feasibility. We will assess level of completeness of all measures and run missing value analysis to determine whether any missing data are missing at random or whether patterns of missing data may indicate a problem with measures.

We will report observed and self-reported bookings, attendances, quit rates set and four-week quits across the intervention and control groups, and the proportion of participants agreeing to allow access to SSS and GP data (where relevant) relating to smoking status and SSS attendance.

We will report on numbers of higher versus lower SES status participants recruited as well as age and gender, and assess using chi-squared analysis whether SES status, age or gender are associated with attrition at baseline, intervention/control access and two-month follow-up.

5. Ethical Considerations

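### Withdrawal deletes every record that could place a participant, so attrition by setting, stage, SES, age and gender omits formal withdrawals

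*Protocol*

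**What the plan says.** **Deletion.** Protocol section 4.9.3 gives participants the right to withdraw their data until the download for analysis (30 June 2019). On a request, the team finds the unique ID and will "then delete all of their data (1-5 as applicable above". Section 5.2 repeats the promise: "all data provided by them will be withdrawn from the dataset and destroyed".

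**What is kept.** Section 4.9.3 names one record: "A datafile logging the date/time of participant withdrawals will held by the lead researcher". It names no setting, stage or participant characteristic.

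**What is in the deleted items.** Under section 4.9.2, item 1 is the eNgage record, with the ID and "responses to randomisation questions and experimental condition assignment". Setting is known through separate project pages, whose purpose is "to enable the unique ID created for each participant to be associated with the type of setting they were recruited from". Items 2 to 5 are the survey answers, postcode and IMD score, web analytics, and stop smoking service data.

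**A conflicting rule.** Section 4.9.2 also says of the eNgage record: "This data will be retained in this full form for six years after the end of the study". It makes no exception for people who withdraw.

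**What the analysis needs.** The primary objective (3.2) is "to estimate recruitment and attrition rates of participants across three settings", and section 4.12 promises: "We will provide percentage rates for attrition across each recruitment setting at each of baseline, intervention/control access, and two-month follow-up". Objective 3.3.5 and section 4.12 also want attrition by SES, age and gender, and section 6 uses these to judge health equity.

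**The concern.** Attrition by setting and stage is half of the primary objective. A person who formally leaves before follow-up is part of that attrition, but the deletion rule removes everything that would show where the person came from, how far they got and which SES, age or gender group they belonged to. They then count neither as recruited nor as lost in any breakdown.

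For people who withdraw before completing follow-up, the error has a known direction: each affected rate looks lower than it was. If requests were more common in one setting or SES group, the comparison between groups would be distorted too, and the equity reading in section 6 rests on that comparison. A later analysis plan cannot mend this, because the data will have been destroyed. The counts have to be taken at the time of withdrawal.

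**Working it through.** **Step 1. The plan's own figure.** Section 4.11 recruits 1.8 participants per day for three months: 1.8 × 90 = 162, and 162 / 3 = 54 per setting. Both reproduce. The protocol gives no expected attrition rate and no expected number of withdrawal requests, so those inputs below are assumptions.

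**Step 2. Where each breakdown is held.**

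| Needed for the attrition tables | Held in | Deleted on withdrawal? |
|---|---|---|
| Setting | eNgage, through the unique ID (item 1) | Yes |
| Gender, self-reported SES | eNgage and baseline survey (items 1, 2) | Yes |
| Age | Baseline survey (item 2) | Yes |
| IMD score | From postcode (item 3) | Yes |
| Stage reached | Consent time (item 1), questionnaires (item 2), analytics (item 4) | Yes |
| Number of withdrawals | Withdrawal log | No |

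The total survives and the breakdown does not.

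**Step 3. Direction of the error.** Let n be the number recruited, L all those lost, and W those among L who withdrew and were deleted.

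- True rate: L / n
- Rate after deletion: (L − W) / (n − W)
- Shortfall: L/n − (L − W)/(n − W) = W(n − L) / [n(n − W)]

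The shortfall is positive whenever W > 0 and L < n.

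**Step 4. Size in one setting** (n = 54; L = 16 assumed, 16/54 = 29.6%).

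| W (assumed) | Rate after deletion | Shortfall |
|---|---|---|
| 1 | 15/53 = 28.3% | 1.3 points |
| 3 | 13/51 = 25.5% | 4.1 points |
| 5 | 11/49 = 22.4% | 7.2 points |

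**Step 5. Size overall** (n = 162; L = 49 assumed, 49/162 = 30.2%). With W = 1: 48/161 = 29.8%, 0.4 points low. With W = 3: 46/159 = 28.9%, 1.3 points low. Here the log permits a full repair: (46 + 3)/(159 + 3) = 49/162 = 30.2%.

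**Step 6. What the log cannot repair.** Suppose 54 retained participants in a setting show 16 lost (29.6%), and the log holds 3 withdrawals of unknown setting. The setting's true rate lies anywhere from 16/54 = 29.6% to (16 + 3)/(54 + 3) = 33.3%. With 5 in the log, the upper end is 21/59 = 35.6%.

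**Step 7. Scale.** At 30% attrition the 95% half-width, 1.96 × √(0.3 × 0.7 / n), is 12.2 points for n = 54 and 7.1 points for n = 162. The shortfalls in steps 4 and 5 are smaller than this sampling error.

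**The case against.** **Few people may be affected.** Section 4.9.3 reaches only those who email the team to withdraw. In an online study most people who leave will simply stop responding, and they keep their records and are counted. This stands. With one request in a setting the shift is about 1 point, well inside sampling error. However, the error is systematic and avoidable, and the protocol offers nothing to show that requests will be rare.

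**The log may hold more than date and time.** The text does not say that it records nothing else. True, but it names no other field, and section 5.2 promises destruction of all data. The interview contact database in the qualitative procedure holds setting, allocation, gender, SES and retention, but only for those who agree to be contacted, so it does not fill the gap.

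**Withdrawing data is not always attrition.** Someone may complete follow-up and then withdraw. That is right, and deleting such a person pushes the rate slightly the other way: 16/53 = 30.2% against 16/54 = 29.6%. The counting rule has to allow for it.

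**Full deletion is a deliberate ethical promise.** It is, and nothing here argues against it. The gap is that no anonymous count is taken first.

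**Stronger readings.** The documents do not support several things that a reader might infer:

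- That overall attrition and recruitment must come out too low. The log gives the total, and nothing says that withdrawals will be left out of it. For the same reason, the stop/go figure of 1.8 per day in section 6 is not undermined.
- That a planned comparison of attrition between arms is spoiled. No such analysis is stated.
- That the error should be set against the ±5% in section 4.11. That figure concerns the recruitment rate; no precision is stated for attrition.
- That the error is several points as a matter of course. That needs withdrawal shares for which the protocol gives no basis.

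**Conclusion.** The point holds for the breakdowns and not for the totals. Followed as written, section 4.9.3 leaves formal withdrawals out of attrition by setting and stage, and by SES, age and gender. For withdrawals before follow-up is complete, those rates are biased low. The amount depends on a number of requests that the protocol does not give: about 1 point for one request and 4 points for three in a setting of 54, if true attrition is near 30%. Overall attrition is recoverable from the log, although section 4.12 does not commit to recovering it.

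Sections 4.9.2 and 4.9.3 also conflict on whether the eNgage record of a withdrawn participant is kept for six years or deleted. Keeping it would preserve setting, gender and SES, but would contradict the promise of deletion.

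This is a cheap improvement. It does not put the trial's main recruitment decision in doubt.

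**What to change.** - **Section 4.9.3:** before deletion, add each withdrawal to aggregate, non-identifying counts by recruitment setting and stage reached, with separate marginal counts by SES group, age band and gender. Allocated arm is optional. Use counts and not one line per person: in a setting of about 54, a line combining several characteristics could single someone out.
- **Participant information, consent statements and section 5.2:** say that an anonymous count remains after withdrawal.
- **Section 4.12:** count withdrawals as recruited, and as attrition at the stage reached unless follow-up had already been completed.
- **Sections 4.9.2 and 4.9.3:** state which rule governs the eNgage consent record of a withdrawn participant.

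The cost is a few sentences and a small tally sheet, settled before recruitment starts. The downside is that a small anonymous count outlives the withdrawal. Separate marginal counts also correct the total loss in each SES, age or gender group but not its split by stage; that is a reasonable price for keeping the counts non-identifying.
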